## **Appendix 14** **Glucocorticoid Toxicity Change Index (cont.)**

### **Cognitive impairment**

- Grade 1: Minor cognitive complaints, no objective findings on mental status examination (i.e., not apparent to the examiner) that were not present before initiating steroids
- Grade 2: New moderate cognitive deficits that were not present before initiating steroids
- Grade 3: Frank delirium

### **Depression**

- Grade 1: Feeling slightly down or depressed and 0–2 mild or occasional additional symptoms of loss of interest, low energy, guilt, poor concentration, insomnia, restlessness, or change in appetite
- Grade 2: Frequent or moderate feelings of being down or depressed and/or 3–4 symptoms of loss of interest, low energy, guilt, poor concentration, insomnia, restlessness, or change in appetite
- Grade 3: Severe constant feeling of being down or depressed and/or 5 or more symptoms of loss of interest, low energy, guilt, poor concentration, insomnia, restlessness, or change in appetite and/or suicidal thoughts

### **INFECTION NOTES**

- No significant infection: No specific infections or serious infections Grade 3 or greater
- Specific infections: Oral or vaginal candidiasis or zoster infections without postherpetic neuralgia or eye involvement

Grade 3: IV antibiotic, anti-fungal, or anti-viral intervention or hospitalization indicated or radiologic or operative intervention indicated or herpes zoster complicated by postherpetic neuralgia or eye involvement

Grade 4 or 5: Life-threatening consequences; urgent intervention indicated or death from infection (Specific Domain)

Signature Page for Protocol - WA29748 - GAZYVA - v4 - Global/Core - Published  
System identifier: RIM-CLIN-483560

Approval Task	[REDACTED]
	Company Signatory 18-Apr-2023 14:24:31 GMT+0000

Official Title: A Randomized, Double-Blind, Placebo-Controlled, Multi-Center Study to Evaluate the Safety and Efficacy of Obinutuzumab in Patients With ISN/RPS 2003 Class III or IV Lupus Nephritis

NCT Number: NCT02550652

Document Date: SAP Version 2: 25-October-2023

STATISTICAL ANALYSIS PLAN

TITLE: A RANDOMIZED, DOUBLE-BLIND,
PLACEBO-CONTROLLED, MULTI-CENTER
STUDY TO EVALUATE THE SAFETY AND
EFFICACY OF OBINUTUZUMAB IN PATIENTS
WITH ISN/RPS 2003 CLASS III OR IV LUPUS
NEPHRITIS

PROTOCOL NUMBER: WA29748

STUDY DRUG: Obinutuzumab (GA101; RO5072759)

VERSION NUMBER: 2

IND NUMBER: 125,054

EUDRACT NUMBER: 2015-002022-39

SPONSOR: F. Hoffmann-La Roche Ltd.

PLAN PREPARED BY: [REDACTED], MSc

DATE FINAL: See electronic date stamp below

DATE AMENDED: See electronic date stamp below
Version 1: 17 August 2018

STATISTICAL ANALYSIS PLAN AMENDMENT APPROVAL

CONFIDENTIAL

This is an F. Hoffmann-La Roche Ltd document that contains confidential information. Nothing herein is to be disclosed without written consent from F. Hoffmann-La Roche Ltd.

STATISTICAL ANALYSIS PLAN AMENDMENT RATIONALE

- The list of exploratory endpoints has been streamlined based on the data availability (Section 2.2.3).
- Data cut and analysis timing have been updated to include all data up to the final database lock (Section 2.4 & 4.4).
- Per protocol population has been removed since the handling method for major protocol deviations that has an impact on the analyses has been discussed in Section 4.6 (Section 4.1).
- Subgroup analyses on the primary endpoint have been updated to include clinically relevant subgroups (Section 4.6.1.7).

Additional minor changes have been made to improve clarity and consistency.

TABLE OF CONTENTS

STATISTICAL ANALYSIS PLAN AMENDMENT RATIONALE	2
1. BACKGROUND	6
2. STUDY DESIGN	6
2.1 Protocol Synopsis	6
2.2 Outcome Measures	6
2.2.1 Primary Efficacy Outcome Measures.....	6
2.2.2 Secondary Efficacy Outcome Measures.....	7
2.2.3 Exploratory Efficacy Outcome Measures.....	7
2.2.4 Safety Outcome Measures	7
2.3 Determination of Sample Size	8
2.4 Analysis Timing.....	8
3. STUDY CONDUCT	8
3.1 Randomization.....	8
3.2 Data Monitoring	9
4. STATISTICAL METHODS	9
4.1 Analysis Populations.....	9
4.1.1 Randomized Population.....	9
4.1.2 Pharmacokinetic-Evaluable Population	9
4.1.3 Safety Population.....	10
4.1.4 Modified Intent-To-Treat Population	10
4.2 Analysis of Study Conduct.....	10
4.3 Analysis of Treatment Group Comparability	11
4.3.1 Demographics.....	11
4.3.2 Disease Characteristics	11
4.4 Data-Cut for Analyses.....	12
4.5 Visit Windows	12
4.6 Efficacy Analysis.....	13
4.6.1 Primary Efficacy Endpoint.....	14
4.6.1.1 Complete Renal Response at Week 52.....	14

Obinutuzumab—F. Hoffmann-La Roche Ltd

Statistical Analysis Plan

WA29748

4.6.1.2	Serum Creatinine.....	15
4.6.1.3	Inactive Urinary Sediment.....	15
4.6.1.4	Urinary Protein to Creatinine Ratio	16
4.6.1.5	Treatment Failure	16
4.6.1.6	Sensitivity analyses	17
4.6.1.7	Subgroup analyses	17
4.6.2	Secondary Efficacy Endpoints	18
4.6.2.1	Overall Renal Response.....	18
4.6.2.2	Biomarkers of Lupus Nephritis.....	18
4.6.2.3	Complete Renal Response at Week 24.....	18
4.6.2.4	Modified Complete Renal Response	19
4.6.3	Exploratory Efficacy Endpoints	20
4.6.3.1	Urine protein creatinine ratio (UPCR)	20
4.6.3.2	Renal Flares	20
4.6.3.3	Physician's Global Assessment (PGA)	20
4.6.3.4	Subject's Global Assessment (SGA)	20
4.6.3.5	Components of CRR.....	20
4.7	Pharmacokinetic and Pharmacodynamic Analyses	20
4.8	Safety Analyses.....	21
4.8.1	Exposure to Study Medication	21
4.8.2	Adverse Events.....	22
4.8.3	Deaths	23
4.8.4	Laboratory Data	23
4.8.4.1	Safety Laboratory Parameters	23
4.8.4.2	Immunoglobulins.....	23
4.8.5	Vital Signs.....	24
4.9	Data Handling Methods	24
4.9.1	Presentation of Data	24
4.9.2	Definitions.....	24
4.9.3	Multiple Values	25
4.10	Missing Data	25
4.11	Interim Analyses	25

4.11.1	Pharmacodynamic Futility Interim Analysis	25
4.11.2	Renal Response Interim Analysis	26
5.	REFERENCES.....	26

LIST OF TABLES

Table 1	Time Windows of Study Days to Assign Study Visit for Urinalysis	12
---------	-----------------------------------------------------------------------	----

LIST OF APPENDICES

Appendix 1	Protocol Synopsis	27
Appendix 2	Schedule of Assessments.....	37
Appendix 3	Imputation Rules for Partial or Missing Dates	41

1. **BACKGROUND**

Study WA29748 (NOBILITY) is a Phase II, parallel-group, double-blind, randomized, placebo-controlled study that aims to evaluate the efficacy and safety of obinutuzumab plus mycophenolate mofetil (MMF) vs. placebo plus MMF in patients with Class III or IV lupus nephritis (LN). The study consists of three periods: a screening period, a 104-week, double-blinded, treatment period followed by an additional B-cell follow-up (BCFU) period extending until the study completion criteria specified in the protocol are met.

To date, two study Clinical Study Reports (CSRs) have been reported for NOBILITY:

- Week 52 CSR (Report No. 1094412)
- Week 104 CSR (Report No. 1102050)

This Statistical Analysis Plan (SAP) describes the statistical methodology and data handling rules to be used for the final CSR reporting, where all available study data in the final locked database will be reported.

The final CSR reporting event and study database lock will occur after end of the study (when all patients have completed or discontinued from the study).

2. **STUDY DESIGN**

2.1 **PROTOCOL SYNOPSIS**

The Protocol Synopsis is provided in [Appendix 1](#). Additional details including the study flowchart and schedule of assessments ([Appendix 2](#)) can be found in the study protocol (version (v) 4.0; 18 April 2023).

2.2 **OUTCOME MEASURES**

2.2.1 **Primary Efficacy Outcome Measures**

The proportion of patients who achieve complete renal response (CRR) will be evaluated at 52 weeks. CRR is defined as meeting all of the following:

- Normalization of serum creatinine as evidenced by the following:
 - Serum creatinine \leq the upper limit of normal (ULN) range of central laboratory values if baseline (Day 1) serum creatinine is above the ULN
 - Serum creatinine \leq 15% above baseline and \leq the ULN range of central laboratory values if baseline (Day 1) serum creatinine is \leq the ULN range of central laboratory values
- Inactive urinary sediment as evidenced by:
 - <10 RBCs/high-power field (HPF); and
 - the absence of red cell casts

- Urinary protein to creatinine ratio <0.5

2.2.2 Secondary Efficacy Outcome Measures

The secondary efficacy outcome measures are as follows:

- Proportion of patients who achieve an overall response at Week 52 (CRR+partial renal response [PRR])
- Proportion of patients that achieve a modified CRR (mCRR1) at Week 52 as defined in Section 4.6.2
- Proportion of patients that achieve a second modified CRR (mCRR2) at Week 52 as defined in Section 4.6.2
- Time to CRR, over the course of 52 weeks.
- Time to overall response (CRR+PRR) over the course of 52 weeks
- Change in anti-double stranded deoxyribonucleic acid (dsDNA) titre, C3 and C4 from baseline at Week 52
- Proportion of patients that achieve a PRR at Week 52
- Proportion of patients who achieve a CRR at Week 24
- Proportion of patients that achieve a third modified CRR (mCRR3) at Week 52 as defined in Section 4.6.2

2.2.3 Exploratory Efficacy Outcome Measures

The protocol presents the complete list of exploratory outcomes. The list below includes exploratory outcomes that are planned to be presented in the final CSR:

- Change in urine protein creatinine ratio (UPCR) from baseline to Week 52
- Proportion of patients experiencing a renal flare over 52 weeks and 104 weeks
- Physician's Global Assessment of disease activity
- Subject's Global Assessment of disease activity
- Proportion of patients who achieve each of the components of the primary endpoint

2.2.4 Safety Outcome Measures

The safety outcome measures are as follows:

- Incidence, type, and severity of adverse events (AEs) and adverse events of special interest (AESI), including infusion reactions, infections, thrombocytopenia, and neutropenia
- Proportion of patients with abnormal vital signs
- Proportion of patients with abnormal laboratory values

Safety will be monitored through regular physical examinations, vital signs, hematologic and chemistry laboratory tests, urinalyses, and incidence and severity of AEs.

In addition, the following will be examined:

- Circulating B cells, T cells, neutrophils, and other cell populations
- Plasma immunoglobulins (total immunoglobulin [Ig], immunoglobulin G [IgG], immunoglobulin M [IgM], and immunoglobulin A [IgA])
- Pregnancy
- Antibody titers for mumps, rubella, varicella, tetanus, influenza, and *Streptococcus pneumoniae*

2.3 DETERMINATION OF SAMPLE SIZE

The primary efficacy endpoint of this study is the proportion of patients that achieve CRR at Week 52. It is estimated that approximately 30% of patients with proliferative LN who are receiving MMF (or equivalent) will achieve a CRR at Week 52 and that the addition of obinutuzumab to MMF (or equivalent) will induce an overall CRR rate of 50% at Week 52. On the basis of these assumptions, a total of 120 patients randomized to obinutuzumab- and placebo-treated groups in a 1:1 ratio (60 patients in each of the obinutuzumab- and placebo-treated groups) will yield approximately 83% power at the two-sided $\alpha=0.2$ significance level using a Cochrane-Mantel-Haenzel (CMH) test, assuming the same CRR proportions across the strata.

No adjustment will be made for dropouts. Patients withdrawing early from the study or meeting the criteria for treatment failure (including rescue therapy) will not receive any additional study drug, but will be monitored for safety for at least 52 weeks after their last dose of study drug, unless they have withdrawn consent. Patients with missing or incomplete data where a status cannot be determined after applying relevant imputation rules (as defined in Section 4.6.1), will be set to non-responders.

2.4 ANALYSIS TIMING

The study database will be locked and the analysis will be after the end of the study (all patients complete or discontinue from the study). All data will be thoroughly cleaned and will form part of the final CSR.

3. STUDY CONDUCT

3.1 RANDOMIZATION

After completing the informed consent form, eligible patients will be enrolled into the study and randomized using a central Interactive Voice/Web Response System (IxRS). Patients will be randomly allocated to receive obinutuzumab or placebo in a 1:1 ratio. Randomization will be performed according to a stratified permuted block design—stratified by race (Afro-Caribbean/African American vs. others) and geographical region (US vs. non-US).

3.2 DATA MONITORING

Safety data and data pertaining to trial conduct will be reviewed by an independent Data Monitoring Committee (iDMC).

In accordance with the study protocol, the iDMC will meet on a regular basis for formal safety data reviews. The first meeting will occur approximately three months after the first study drug infusion in the first enrolled patient. The iDMC will then meet formally, approximately every three to six months, to review current safety data.

In addition to the regularly scheduled safety reviews, an unscheduled review of the data may be performed at the request of the iDMC or study team, on the basis of a perceived concern for patient safety.

The iDMC will review the results of a planned futility analysis based on the expected pharmacodynamic (PD) effects of obinutuzumab (i.e., CD19⁺ B-cell depletion as measured by a high sensitivity flow cytometry assay), which is scheduled to be undertaken after 30 subjects have been assigned obinutuzumab and have had their Day 28 CD19⁺ B-cell count performed.

In addition, an interim efficacy analysis to evaluate CRR will be conducted when the last patient has attended the Week 24 visit. This interim analysis is for Phase III planning purposes only and will have no impact on the progression of this study. The interim analysis will be performed by the independent Data Coordinating Center (iDCC) and interpreted by members of the iDMC.

The Sponsor's study team will have no direct contact with the iDMC during the trial conduct except for the scheduled open sessions of the iDMC.

Further details can be found in the iDMC charter.

4. STATISTICAL METHODS

All analyses, summaries, and listings will be performed using SAS[®] software (v 9.4 or later).

4.1 ANALYSIS POPULATIONS

4.1.1 Randomized Population

The randomized population will include all patients randomized into the study.

4.1.2 Pharmacokinetic-Evaluable Population

The pharmacokinetic-evaluable population (PK population) will include all patients randomized to — and received any dose of — obinutuzumab given as study medication,

have at least one post-dose pharmacokinetic (PK) sample that is evaluable, and have no major protocol deviations that would impact the PK results.

4.1.3 Safety Population

The safety population will include all randomized patients who received any part of an infusion of study drug. Patients who received the incorrect therapy throughout the study from that assigned at randomization will be reported under the therapy actually received. Patients who were not randomized but who received study drug will be included in the safety population and reported under the therapy actually received.

Patients receiving at least one dose of both active study treatments during the study (e.g., in error, or in the unlikely event of crossing over) will be reported under the original treatment received. Patients who received obinutuzumab as rescue therapy will be reported under the original treatment received before the rescue.

All safety analyses will be performed using the safety population.

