## **6. STATISTICAL CONSIDERATIONS AND ANALYSIS PLAN**

All efficacy outcomes will be analyzed according to the modified intent-to-treat principle and will include all randomized patients who have received any amount of study drug. Patients will be grouped according to randomized (assigned) treatment, rather than treatment received.

Treatment period data will be locked after all patients have completed the Week 52 visit. The primary efficacy and safety analyses will be performed on data for all patients through the Week 52 assessments or early discontinuation.

Safety assessments will be performed on patients who receive study medication. In all safety analyses, patients will be grouped according to the treatment that patients actually received rather than the treatment assigned.

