### **6.5 SAFETY ANALYSES**

The safety analyses will include all randomized patients who received any study drug, with patients grouped according to the treatment actually received.

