4.8 SAFETY ANALYSES

The safety analysis will be performed on the safety population as defined in Section 4.1.3. Analyses of safety data will include patients up to the point of receipt of non-corticosteroid rescue only. All safety data including the post-rescue data will be summarized separately for key safety outputs.

All safety outputs will include cumulative data to the final database lock. In addition, data collected after Week 104 will be summarized separately for key safety outputs to understand the Safety events occurring during the B-cell follow-up period only. Safety data will be summarized by treatment groups.

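### SAP 4.1.3 keeps a patient who received both treatments under the first one received, so events after a mistaken obinutuzumab dose can be counted as placebo events

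*SAP*

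**What the plan says.** SAP 4.1.3 has three rules for patients whose treatment departs from the allocation.

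- Wrong treatment all the way through: "Patients who received the incorrect therapy throughout the study from that assigned at randomization will be reported under the therapy actually received".
- A mixture of treatments. The patients covered are described as "Patients receiving at least one dose of both active study treatments during the study", and the rule for them is "e.g., in error, or in the unlikely event of crossing over) will be reported under the original treatment received".
- Obinutuzumab as rescue: "Patients who received obinutuzumab as rescue therapy will be reported under the original treatment received before the rescue".

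SAP 4.8 adds a data cut-off that applies to rescue: "Analyses of safety data will include patients up to the point of receipt of non-corticosteroid rescue only". Key outputs that include post-rescue data are shown separately. Safety outputs otherwise run cumulatively to the final database lock. No cut-off is given for a dosing error.

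Protocol Section 6 states: "In all safety analyses, patients will be grouped according to the treatment that patients actually received rather than the treatment assigned". Protocol 6.5 repeats the rule for the safety analyses, "with patients grouped according to the treatment actually received". Neither section says where a patient who received both belongs.

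**The concern.** The purpose of as-treated grouping in a safety analysis is that events which obinutuzumab may have caused appear in the obinutuzumab column. The mixed-receipt rule can do the reverse. A patient who starts on placebo and is later given obinutuzumab by mistake stays under placebo for every infusion reaction, infection or cytopenia that follows. The first treatment received will usually be the one assigned, so for these patients the rule comes close to grouping as randomized.

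The SAP protects the placebo column against obinutuzumab given as rescue by cutting the data there. It gives no such protection against obinutuzumab given in error. The protocol's own background suggests that one infusion could matter. Protocol 5.1.1 says infusion reactions arose mainly with the first 1000 mg, and Protocol 5.1.6 says B-cell recovery took more than 12 months in most cases in earlier obinutuzumab studies. Protocol 4.2 foresees that dosing errors may need investigating, since it allows comparator PK samples to be assayed for that reason.

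The wording is also a problem. The rule speaks of two active study treatments, but the blinded comparison is obinutuzumab against placebo. Read literally, it may not cover the one mixture that can occur, and a programmer would have to guess.

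**Working it through.** The plan states no figure on this point, so there is none to reproduce. The check compares the rules and then sizes the effect.

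**Where each case goes**

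| Case | Reporting group | Data cut-off |
|---|---|---|
| Wrong treatment throughout | Treatment received | None needed |
| Placebo, then obinutuzumab as rescue | Placebo | At rescue |
| Placebo, then obinutuzumab in error | Placebo | None |
| Obinutuzumab on Day 1 in error, then placebo | Obinutuzumab | None |

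Only the third row puts events after obinutuzumab into the placebo column of the main tables.

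**Opportunities.** Inputs: 60 patients per arm (SAP 2.3) and infusions on Days 1, 15, 168 and 182 (Protocol 4.3.2.1). A Day 1 error makes obinutuzumab the first treatment received, so only the three later infusions count: 60 x 3 = 180 at most.

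**Follow-up affected.** Share of follow-up on or after the wrong infusion = (end day - infusion day + 1) / end day, for a patient followed to the end day.

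| Error on | To Week 52 (Day 364) | To Week 104 (Day 728) |
|---|---|---|
| Day 15 | 350/364 = 96% | 714/728 = 98% |
| Day 168 | 197/364 = 54% | 561/728 = 77% |
| Day 182 | 183/364 = 50% | 547/728 = 75% |

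All of this time counts as placebo exposure. The rates per 100 patient-years in SAP 4.8.2 are affected as well as the percentages.

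**Shift in the risk difference (obinutuzumab minus placebo).** The base rates and k, the number of mis-dosed patients, are assumptions. Each of the k patients is taken to have one event, after the obinutuzumab dose.

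- First-received rule: a/60 - (b + k)/60.
- Any-obinutuzumab rule: (a + k)/(60 + k) - b/(60 - k).

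| Assumed a, b | k | First-received | Any obinutuzumab | Shift (points) |
|---|---|---|---|---|
| 12, 6 | 1 | 12/60 - 7/60 = 8.3 | 13/61 - 6/59 = 11.1 | 2.8 |
| 6, 6 | 1 | 6/60 - 7/60 = -1.7 | 7/61 - 6/59 = 1.3 | 3.0 |
| 12, 6 | 3 | 12/60 - 9/60 = 5.0 | 15/63 - 6/57 = 13.3 | 8.3 |

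With equal base rates, a single patient changes the sign of the difference.

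**The case against.** The strongest objection is that no protocol rule is broken. A reader might infer that SAP 4.1.3 contradicts the protocol's as-treated rule, but the documents do not support that. The protocol contrasts treatment received with treatment assigned and is silent on mixed receipt. Grouping by the first treatment received is still grouping by a treatment received, and the SAP follows the protocol for patients wrongly treated throughout. This part of the objection stands.

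The size is also easy to overstate. A reader might count 60 x 4 = 240 infusions at risk, but the Day 1 infusion does not belong in the count. A reader might also add 1/60 to one arm and 1/60 to the other and get 3.3 points, but that ignores the denominators becoming 61 and 59. Nor do the documents show that any obinutuzumab event was placed under placebo in this trial. No mis-dosed patient is reported, and the SAP itself regards crossing over as unlikely.

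The plan also makes such cases traceable. Major protocol deviations are listed (SAP 4.2), all adverse events are listed (SAP 4.8.2), and obinutuzumab exposure is taken from the administration log and the actual treatment received (SAP 4.8.1). This helps a careful reader but does not correct the summary tables. A patient could count as exposed to obinutuzumab in one table while the later events sit under placebo in another.

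Two further objections bear on the remedy. Moving a patient wholesale to obinutuzumab would carry the placebo person-time along and dilute the obinutuzumab rate. Also, the Week 52 and Week 104 reports already exist (SAP 1), so a new grouping could differ from them. Both are fair, and the fix has to meet them.

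**Conclusion.** The point holds as a minor one. Followed exactly, SAP 4.1.3 together with SAP 4.8 counts events and person-time after a mistaken obinutuzumab dose under placebo, in the direction that can hide an obinutuzumab excess. It fills a gap that the protocol leaves, in a way that defeats the purpose of as-treated grouping.

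The size is conditional. It needs at least one placebo-first patient given obinutuzumab in error at one of at most 180 later infusions, and the documents do not say whether there was one. Given one such patient with an event, the risk difference moves by roughly 3 points (2.8 to 3.0 under the assumed base rates). If there was none, the tables are unaffected and only the wording needs correcting. The efficacy analyses are not involved, because the modified intent-to-treat population is grouped as randomized.

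**What to change.** Amend SAP 4.1.3 as follows.

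1. Replace the phrase that calls both study treatments active with one that names obinutuzumab and placebo.
2. Report any patient with at least one non-rescue obinutuzumab dose under obinutuzumab for safety. Leave the rescue rule and its cut-off as they are.
3. Attribute events and person-time before the first obinutuzumab dose to placebo, so that rates per 100 patient-years are not diluted. In the tables of percentages, count the patient once, under obinutuzumab, for events from that dose on, and show earlier events in the listing as placebo events.
4. State the number of such patients in the final report, including if it is zero, and list them. If there are any, also show the tables grouped by first treatment received, for consistency with the Week 52 and Week 104 reports.

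The cost is a short SAP change, one count and a small amount of programming. The one drawback is a possible difference from tables already reported if any such patient exists, which is why both groupings would then be shown.
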